5.14.5. Clinical Laboratory Assessments

Descriptive summaries of selected (quantitative) clinical laboratory results will be presented by treatment group and study visit. Laboratory values outside the normal range for each systematically collected hematology, blood chemistry, and urinalysis parameter will be identified. Each subject's hematology, blood chemistry, and quantitative urinalysis values will be flagged as "low" (below the lower limit of normal/LLN), "normal" (within the normal range), or "high" (above the upper limit of normal/ULN) relative to the normal ranges of the central laboratory. Each subject's qualitative urinalysis results will be flagged as "normal" or "abnormal". In addition, the severity of laboratory abnormality will be graded based on toxicity criteria specified in [Section 9.8](#) in reference to Common Terminology Criteria for Adverse Events (CTCAE) Version 5.0. The result of each laboratory test for individual subjects will be presented in a listing with the normal range defined by the central laboratory, the status relative to the normal range, and the toxicity grade.

Shift table will be used to summarize shifts from baseline toxicity grades to greatest (worst) treatment-emergent laboratory toxicity grade. For hematology and, blood chemistry, and quantitative urinalysis parameters that toxicity grade was not defined, a shift table for each laboratory test will be based on the shift from baseline high/normal/low status to the status of the maximum post-baseline value and the minimum post-baseline value (including test results from unscheduled visits, if any). Similarly, for qualitative urinalysis parameters, shifts from baseline normal/abnormal status to the worst post-baseline status will be summarized.

The number and percentage of subjects who have post-baseline elevations in liver transaminase (alanine aminotransferase [ALT] or aspartate aminotransferase [AST]) or bilirubin abnormalities in relation to fold above the upper limit of normal will be summarized according to the Food and Drug Administration's Premarketing Clinical Evaluation on Drug-Induced Liver Injury Guidance for Industry ([FDA 2009](#)). Abnormal hepatic laboratory values will be categorized and evaluated for any occurrence among all post-baseline assessments (where "and" in the bulleted list below indicates elevations occurring at the same visit). Within each laboratory parameter grouping, a subject may be counted once per elevation criteria using the worst-case result.

That is, a subject with a worst case ALT elevation $> 5 \times$ the ULN would be counted once in the ALT $> 3 \times$ ULN category and once in the ALT $> 5 \times$ ULN category, regardless of how many ALT elevations the subject had that met the $> 3 \times$ ULN and $> 5 \times$ ULN elevation criteria.

- ALT and/or AST $> 3 \times$ ULN and total bilirubin > 1.5 or $2 \times$ ULN
- AST $> 3, 5, 10, 20 \times$ ULN
- ALT $> 3, 5, 10, 20 \times$ ULN
- Total bilirubin $> 1.5, 2 \times$ ULN
- Alkaline phosphatase (ALP) $> 1.5 \times$ ULN

In addition, an eDISH plot, a shift plot showing liver safety panel tests over time (baseline vs. post-baseline), and distribution plots of ALT, AST, ALP, and bilirubin over time will be produced to aid identification of any potential cases (Merz M. et. al. 2014). The plots to be included are the scatter plot of maximum transaminase versus maximum bilirubin, the liver test safety panel over time, and the distribution of ALT by time. The distribution plots for AST, ALP, and bilirubin will use the same format as used for ALT.

5.14.6. Vital Signs

Vital signs include systolic and diastolic blood pressures, heart rate, and body temperature. Supine (after 5 minutes of rest) and standing (2 minutes after rising from supine to standing) measurements will be obtained for blood pressure and heart rate. Duplicate readings of supine blood pressure and heart rate will be taken. The duplicate values will be individually recorded, and the values will be averaged by the sponsor for the time point assessment. Orthostatic changes will be derived using standing and supine values. Body temperature will be obtained once, at the time of the first blood pressure measurement.

5.14.6.1. Blood Pressure and Heart Rate

Blood pressure and heart rate measurements and corresponding changes from baseline will be summarized by treatment group, position (if applicable), and visit using descriptive statistics. The distribution of diastolic and systolic blood pressure over time will be evaluated using box plots. Average records will be used for the analysis where available.

Number and percent of subjects with at least one of the out-of-range value in blood pressure and heart rate will be summarized by treatment group based on the following criteria:

Supine Systolic Blood Pressure (mmHg)

- < 80 mmHg
- < 90 mmHg
- > 140 mmHg
- > 160 mmHg
- > 200 mmHg

Change from Baseline in Supine Systolic Blood Pressure (mmHg)

- < -20 mmHg
- < -10 mmHg
- > 10 mmHg
- > 20 mmHg

Orthostatic Systolic Blood Pressure (mmHg)

- ≥ 20 mmHg decrease upon standing compared with supine position
- ≥ 20 mmHg increase upon standing compared with supine position

Supine Diastolic Blood Pressure (mmHg)

- < 50 mmHg
- > 90 mmHg
- > 100 mmHg
- > 120 mmHg

Change from Baseline in Supine Diastolic Blood Pressure (mmHg)

- < -15 mmHg
- < -10 mmHg
- > 10 mmHg
- > 25 mmHg

Orthostatic Diastolic Blood Pressure (mmHg)

- ≥ 10 mmHg decrease upon standing compared with supine position
- ≥ 10 mmHg increase upon standing compared with supine position

Supine Heart Rate (beats/min)

- < 50 bpm
- < 60 bpm
- > 100 bpm and ≤ 120 bpm
- > 120 bpm

The number and percentage of the out-of-range values will also be summarized by treatment phase (titration and maintenance phase). For supine measurements, the average of the duplicate will be used to determine out-of-range status, unless in isolated cases where only a single measurement was taken.

5.14.6.2. Body Weight

Body weight measurements at baseline and at the end of treatment with corresponding changes from baseline will be summarized by treatment group using descriptive statistics.

Number and percent of subjects with out-of-range body weight changes will be summarized based on the following criteria:

- Decrease from Baseline 7% or more (i.e. change from baseline $\leq -7\%$)
- Increase from baseline 7% or more (i.e. change from baseline $\geq 7\%$)

5.14.6.3. Temperature

Temperature and corresponding changes from baseline will be summarized by treatment group, and visit using descriptive statistics. Number and percent of subjects with out-of-range temperature will be summarized based on the following criteria:

- $>38.0\text{ }^{\circ}\text{C}$
- $<36.0\text{ }^{\circ}\text{C}$

5.14.7. Electrocardiograms (ECGs)

Single or triplicate 12 lead ECGs will be obtained during the trial. All ECG recordings will be obtained after the subject has been supine and at rest for at least 5 minutes. A triplicate set of ECGs is 3 consecutive ECGs collected 1 to 2 minutes apart over a 5 minute period. Any values taken in triplicate will be averaged for analysis. ECGs and corresponding changes from baseline will be summarized by treatment group and visit using descriptive statistics. Average records will be used for the analysis where available.

The number and percentage of subjects who experience any post-baseline occurrence of potentially clinically significant corrected QT values using Fridericia's method (QTcF) will be summarized by treatment group. These presentations will include QTcF values > 450 to ≤ 480 , > 480 to ≤ 500 , and > 500 msec; or changes of > 30 to ≤ 60 or > 60 msec ([FDA, 2005](#)). For this categorization, the average of triplicate values will be utilized rather than the individual values comprising the triplicate measurement. An out-of-range categorical tabulation will also be presented for the subgroup of U.S subjects.

Additionally, a distribution plot of QTcF over time will be presented as an aid in identification of any possible time trend and outliers.

A substudy to evaluate the effect of tavapadon on the QT interval using C-QT modelling is also included in this trial. Matched triplicate ECGs and plasma tavapadon concentrations that are collected at preselected sites will be used to characterize the effects of tavapadon on the QT interval. The analysis plan is summarized separately.

5.14.8. Physical and Neurological Examinations

Physical and Neurological examination data will be listed.

5.14.9. Columbia-Suicide Severity Rating Scale (C-SSRS)

The maximum post-baseline results from the C-SSRS will be summarized. The maximum of each subscale (suicidal ideation [Categories 1-5], suicidal behavior [Categories 6-10], suicidal ideation or behavior [Categories 1-10], and self-injurious behavior without suicidal intent) will be presented. The number of patients with suicide-related treatment-emergent events, treatment-emergent suicidal ideation, and suicidal behavior, based on a comparison of the C-SSRS at baseline and/or previous lifetime experience to maximum C-SSRS scores across all post-baseline assessments will be provided. All C-SSRS elements will be reflected in a listing.

5.15. Pharmacokinetics

Plasma concentrations of tavapadon and CV-0000053 (metabolite) will be determined using a validated LC-MS/MS method. PK data listings will be presented for the PK population. PK summary tables and mean figures will be presented using the PK analysis set.

5.15.1. Pharmacokinetic Data Analysis

Plasma concentrations of tavapadon and CV-0000053 (metabolite) will be summarized separately using descriptive statistics by visit. Plasma concentrations of tavapadon and CV-0000053 that are <LLOQ will be reported as 'BLQ' in the data listings. Plasma concentrations that are BLQ will be treated as 0 for calculation of descriptive statistics. The geometric mean, however, will be calculated by imputing BLQ values as $\frac{1}{2}$ LLOQ. If the calculated mean concentration is below the limit of quantitation, the mean will be reported as BLQ and the SD and CV% shall be reported as not determined (ND). Mean plasma concentrations (SD) of tavapadon and CV-0000053 will also be plotted versus time (in both linear and semi-logarithmic scale) based on nominal visit.

5.16. Protocol Deviations

All protocol deviations will be reviewed by the project team prior to database lock and unblinding to identify subjects with important protocol deviations. The number and percentage of subjects with important deviations will be tabulated by treatment and further tabulated by category and treatment. All deviations from the protocol will be listed by category along with a description and any additional comments.

6. CHANGES IN THE PLANNED ANALYSES

Should any deviations from the analyses specified in the final approved (prior to database lock and unblinding) statistical analysis plan arise, such deviations will be documented in the final clinical study report.

7. REVISION HISTORY

Date	Revision	Rationale

9. APPENDICES

9.1. Schedule of Assessments

Table 5: Schedule of Assessments

Trial Period:	Screen	Baseline	Treatment									Safety Follow-up ^a
Trial Week:	-4 to -1	1	2	5	8	11	14	18	22	26	27 ^b	31
Trial Day:	-31 to -1	1	14±3	35±3	56±3	77±3	98±3	126±3	154±3	182±3	189±3	217±3
Visit/Contact:	Visit 1	Visit 2	Visit 3	Visit 4	Visit 5	Visit 6	Visit 7	Visit 8	Visit 9	Visit 10	Visit 11 (EOT/ET)	Telephone ^c
Entrance and History												
Informed consent ^d	X											
Eligibility criteria	X	X										
Demography	X											
Psychiatric history ^e	←-----→											
Medical history ^e	←-----→											
Alcohol/illicit drug use inquiry	X											
Modified Hoehn and Yahr stage	X						X			X	X	
MoCA	X											
Randomization		X										
Efficacy and Other Endpoint Assessments												
MDS-UPDRS ^f	X	X		X	X	X	X	X	X	X	X	
CGI-S		X		X	X	X	X	X	X	X	X	
CGI-Ig ^g				X	X	X	X	X	X	X	X	
PGIC ^g				X	X	X	X	X	X	X	X	
PDQ-39		X								X	X	
Schwab and England ADL		X		X	X	X	X	X	X	X	X	
EQ-5D-5L		X					X			X	X	
Safety Assessments												
ESS		X	X	X	X	X	X	X	X	X	X	

Trial Period:	Screen	Baseline	Treatment										Safety Follow-up ^a
			2	5	8	11	14	18	22	26	27 ^b	31	
Trial Week:	-4 to -1	1	14±3	35±3	56±3	77±3	98±3	126±3	154±3	182±3	189±3	217±3	
Trial Day:	-31 to -1	1	14±3	35±3	56±3	77±3	98±3	126±3	154±3	182±3	189±3	217±3	
Visit/Contact:	Visit 1	Visit 2	Visit 3	Visit 4	Visit 5	Visit 6	Visit 7	Visit 8	Visit 9	Visit 10	Visit 11 (EOT/ET)	Telephone ^c	
QUIP-RS		X	X	X	X	X	X	X	X	X	X	X	
C-SSRS ^h	X	X	X	X	X	X	X	X	X	X	X	X	
Physical/neurological examination ⁱ	X											X	
Weight	X	X										X	
Vital signs ^j	X	X	X	X	X	X	X	X	X	X	X	X	
12-Lead ECGs													
US sites													
Single ECG	X												
Three sets of triplicate ECGs ^k (-45, -30, and -15 min prior to first dose of IMP)		X											
One set of triplicate ECGs ^{k,l}		X		X		X	X		X		X		
Non-US sites													
Single ECG ^l	X	X		X		X	X		X		X		
One set of triplicate ECGs ^{k,l} prior to first dose of IMP		X											
Eye examination						X ^v					X ^w		
Prior/concomitant medications	←-----→												
Adverse events ^m		←-----→											
Laboratoryⁿ													
Safety laboratory blood sample	X	X				X			X		X		
Prolactin level		X ^u									X ^u		
Serology (HIV, HbsAg, and HCV)	X												
Dipstick urinalysis ^o	X	X				X			X		X		

Trial Period:	Screen	Baseline	Treatment									Safety Follow-up ^a
			2	5	8	11	14	18	22	26	27 ^b	
Trial Week:	-4 to -1	1	2	5	8	11	14	18	22	26	27 ^b	31
Trial Day:	-31 to -1	1	14±3	35±3	56±3	77±3	98±3	126±3	154±3	182±3	189±3	217±3
Visit/Contact:	Visit 1	Visit 2	Visit 3	Visit 4	Visit 5	Visit 6	Visit 7	Visit 8	Visit 9	Visit 10	Visit 11 (EOT/ET)	Telephone ^c
Serum pregnancy test ^p	X											
Urine dipstick pregnancy test ^p		←-----→										
Urine drug screen ^q	X	←-----→									X	
Plasma PK sample ^r		X	X	X	X	X	X	X	X	X	X	
Future biospecimen research blood sample ^s		X										
IMP Administration and Compliance ^t												
Dispense IMP		X	X	X	X	X	X	X	X	X		
Assess IMP compliance			X	X	X	X	X	X	X	X	X	

[figure not shown]
Abbreviations: ADL = activities of daily living, CGI-I = Clinical Global Impression – Improvement, CGI-S = Clinical Global Impression – Severity of Illness, C-SSRS = Columbia-Suicide Severity Rating Scale, ECG = electrocardiogram, eCRF = electronic case report form, EQ-5D-5L = EuroQol 5 Dimension 5 Level, ESS = Epworth Sleepiness Scale, EOT = end of treatment, ET = early termination, HbsAg = hepatitis B surface antigen, HCV = hepatitis C virus, HIV = human immunodeficiency virus, IMP = investigational medicinal product [REDACTED], MDS-UPDRS = Movement Disorder Society – Unified Parkinson’s Disease Rating Scale, MoCA = Montreal Cognitive Assessment, PDQ-39 = 39-Item Parkinson’s Disease Questionnaire, PGIC = Patient Global Impression of Change, PK = pharmacokinetic, QUIP-RS = Questionnaire for Impulsive-Compulsive Disorders in Parkinson’s Disease-Rating Scale.

- a. Subjects who prematurely discontinue from the trial or who are not eligible for or choose not to participate in the open-label extension trial (Protocol CVL-751-PD-004) are to participate in the 4-week Safety Follow-Up Period. Subjects who proceed into the open-label extension trial will go directly into that trial and will not complete the Safety Follow-Up Period.
- b. The assessments scheduled for the Week 27 visit are to be performed for any subject who prematurely discontinues from the trial.
- c. Contact with subjects via telephone call or other means of communication to check on their status.
- d. Informed consent must be obtained before any trial-related procedures are performed.
- e. Medical occurrences that begin before the start of IMP dosing but after obtaining informed consent will be recorded as medical and/or psychiatric history.
- f. MDS-UPDRS Parts I, II, and III will be conducted before the first dose of IMP at the Baseline Visit and at ~2 to ~6 hours after dosing (at home) at clinic visits during the Treatment Period.
- g. All responses will be relative to the subject’s condition at the Baseline Visit (Day 1) before the first dose of IMP.
- h. The “Baseline/Screening” C-SSRS form will be completed at the Screening Visit to determine eligibility. The “Since Last Visit” C-SSRS form will be completed at the Baseline Visit to ensure that the subject continues to qualify for the trial and at all visits after the Baseline Visit.
- i. Full physical and neurological examinations should be completed at the Screening Visit and at Week 27. The physical examination should include height at the Screening Visit only. Physical and/or neurological examinations can be done at any time point during the trial at the investigator’s discretion.

Trial Period:	Screen	Baseline	Treatment									Safety Follow-up ^a
Trial Week:	-4 to -1	1	2	5	8	11	14	18	22	26	27 ^b	31
Trial Day:	-31 to -1	1	14±3	35±3	56±3	77±3	98±3	126±3	154±3	182±3	189±3	217±3
Visit/Contact:	Visit 1	Visit 2	Visit 3	Visit 4	Visit 5	Visit 6	Visit 7	Visit 8	Visit 9	Visit 10	Visit 11 (EOT/ET)	Telephone ^c

- j. Duplicate measurements of blood pressure and heart rate will be obtained in supine (after 5 minutes of rest) and 1 measurement of blood pressure and heart rate will be obtained on standing (2 minutes after rising from supine to standing).
- k. A triplicate set of ECGs is 3 consecutive ECGs collected 1 to 2 minutes apart over a 5-minute period.
- l. The postdose ECGs (triplicate set for US sites at all visits and single for non-US sites at all visits) will be obtained at ~1 hour after administration of the first dose of IMP at the Baseline Visit just prior to the time of collection of the PK blood sample. ECGs at all postbaseline visits will be obtained just prior to the time of collection of the PK blood sample.
- m. All adverse events that are observed by trial personnel or volunteered by the subject in response to open-ended questioning will be recorded from the first dose of IMP through the end of the Safety Follow-up Period. Serious adverse events will be followed until resolution.
- n. Individual sites may require subjects to have COVID-19 testing done prior to randomization. COVID-19 testing may be performed after randomization per the principal investigator's discretion.
- o. Dipstick urinalysis results are not to be recorded on the eCRFs; any clinically significant abnormality should be captured as an adverse event.
- p. For women of childbearing potential only. All positive urine dipstick pregnancy tests must be confirmed by a serum test. Pregnancy tests can be performed at any time during the trial at the discretion of the investigator. Female subjects with exclusively the same sex partners may not be required to have pregnancy tests per investigator discretion; confirmation with the medical monitor is required.
- q. A urine drug screen is required at screening (see exclusion criteria for exclusions based on the urine drug screen) and may be obtained at other times, at investigator discretion, if use of prohibited drugs is suspected.
- r. PK samples will be collected ~1 hour after administration of the first dose (Day 1) and at the clinic visits at the end of Weeks 5, 11, 14, 22, and 27 just after ECG acquisition at each time point. The date and time of the most recent dose, the dose amount, and the time of the blood draw will be recorded.
- s. Future biospecimen research sample is optional and is to only be collected if signed consent is obtained from the subject.
- t. The first dose of IMP (at the Baseline Visit) will be taken in the clinic; all other doses will be taken on an outpatient basis. Subjects will be instructed to bring their IMP to each clinic visit. Compliance will be assessed through self-reporting by the subject and by tablet count.
- u. Prolactin results will be blinded.

Trial Period:	Screen	Baseline	Treatment									Safety Follow-up ^a
Trial Week:	-4 to -1	1	2	5	8	11	14	18	22	26	27 ^b	31
Trial Day:	-31 to -1	1	14±3	35±3	56±3	77±3	98±3	126±3	154±3	182±3	189±3	217±3
Visit/Contact:	Visit 1	Visit 2	Visit 3	Visit 4	Visit 5	Visit 6	Visit 7	Visit 8	Visit 9	Visit 10	Visit 11 (EOT/ET)	Telephone ^c

9.2. EQ-5D-5L Dimensions

EQ-5D-5L Dimensions (UK English Sample Version)

Dimensions	Item	Coded Value
Mobility	I have no problems in walking about	1
	I have slight problems in walking about	2
	I have moderate problems in walking about	3
	I have severe problems in walking about	4
	I am unable to walk about	5
Self-care	I have no problems washing or dressing myself	1
	I have slight problems washing or dressing myself	2
	I have moderate problems washing or dressing myself	3
	I have severe problems washing or dressing myself	4
	I am unable to wash or dress myself	5
Usual activities (e.g., work, study, housework, family or leisure activities)	I have no problems doing my usual activities	1
	I have slight problems doing my usual activities	2
	I have moderate problems doing my usual activities	3
	I have severe problems doing my usual activities	4
	I am unable to do my usual activities	5
Pain/discomfort	I have no pain or discomfort	1
	I have slight pain or discomfort	2
	I have moderate pain or discomfort	3
	I have severe pain or discomfort	4
	I have extreme pain or discomfort	5
Anxiety/depression	I am not anxious or depressed	1
	I am slightly anxious or depressed	2
	I am moderately anxious or depressed	3
	I am severely anxious or depressed	4
	I am extremely anxious or depressed	5

9.3. Columbia-Suicide Severity Rating Scale (C-SSRS) Suicidal Ideation and Suicidal Behavior Scores

The C-SSRS is comprised of 10 categories with binary responses. The 10 categories include:

Category 1 – Wish to be Dead

Category 2 – Non-specific Active Suicidal Thoughts

Category 3 – Active Suicidal Ideation with Any Methods (Not Plan) without Intent to Act

Category 4 – Active Suicidal Ideation with Some Intent to Act, without Specific Plan

Category 5 – Active Suicidal Ideation with Specific Plan and Intent

Category 6 – Preparatory Acts or Behavior

Category 7 – Aborted Attempt

Category 8 – Interrupted Attempt

Category 9 – Actual Attempt (non-fatal)

Category 10 – Completed Suicide

Categories 1-5 represent Suicidal Ideation and categories 6-10 represent Suicidal Behavior. Each category is scored as 1 if there is a positive response in the category and a 0 if there are no positive responses in the category.

- Self-Injurious Behavior Without Suicidal Intent During Treatment

A subject will be categorized as having self-injurious behavior without suicidal intent if there is an occurrence of non-suicidal self-injurious behavior on the C-SSRS – Since Last Visit eCRF at any post-baseline visit.

- Baseline C-SSRS Score

Baseline represents the pre-treatment assessment of recent history, with elements of suicidal ideation assessed over the prior 6 months and elements of suicidal behavior assessed over the prior 2 years. It is scaled from 0 (no suicidal ideation or behavior) to 10 (completed suicide)

- Treatment-Emergent Suicide-Related Event

A subject will be categorized as having a treatment-emergent suicide-related event if at least one post-baseline suicidal ideation or suicidal behavior score is greater than 0.

- Treatment-Emergent Suicidal Ideation Compared to Recent History

A subject will be categorized as having treatment-emergent suicidal ideation compared to recent history when there is at least one post-baseline suicidal ideation score > 0 and is an increase from baseline. Lifetime scores are not considered for baseline suicidal ideation responses.

- Treatment-Emergent Serious Suicidal Ideation Compared to Recent History

A subject will be categorized as having treatment-emergent serious suicidal ideation compared to recent history if the baseline score was < 4 and the post-baseline suicidal ideation score increases to 4 or 5. Lifetime scores are not considered for baseline suicidal ideation responses.

- Emergence of Serious Suicidal Ideation Compared to Recent History

A subject will be categorized as having emergence of serious suicidal ideation compared to recent history if baseline score was 0 (no suicidal ideation) and post-baseline C-SSRS suicidal ideation score is either 4 or 5. Lifetime scores are not considered for baseline suicidal ideation responses.

- Emergence of Suicidal Behavior Compared to all Prior History

A subject will be categorized as having emergence of suicidal behavior compared to all prior history if there had been no suicidal behavior in Categories 6-10 reported at any pre-treatment assessment, including responses to lifetime history questions, and there is at least one positive post-baseline C-SSRS assessment in Categories 6-10. 'All Prior History' represents lifetime history.

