8.	Subjects who answer “yes” on the C-SSRS Suicidal Ideation Item 4 or Item 5 (Active Suicidal Ideation with Some Intent to Act, Without Specific Plan, or Active Suicidal Ideation with Specific Plan and Intent) and whose most recent episode meeting the criteria for C-SSRS Item 4 or Item 5 occurred within the last 6 months, OR Subjects who answer “yes” on any of the 5 C-SSRS Suicidal Behavior Items (actual attempt, interrupted attempt, aborted attempt, preparatory acts, or behavior) and whose most recent episode meeting the criteria for any of these 5 C-SSRS Suicidal Behavior Items occurred within the last 2 years, OR Subjects who, in the opinion of the investigator, present a serious risk of suicide.
9.	Subjects with substance abuse or dependence disorder, including alcohol, benzodiazepines, and opioids, but excluding nicotine, within the past 6 months (180 days).
10.	Subjects with dementia or cognitive impairment that, in the judgement of the investigator, would exclude the subject from understanding the ICF or participating in the trial.
11.	Subjects with any condition that could possibly affect drug absorption, including bowel resections, bariatric weight loss surgery, or gastrectomy (this does not include gastric banding).
12.	Subjects who have a positive result for HIV antibodies, HbsAg, or HCV antibodies at screening. Note: Subjects who were previously infected with hepatitis C but have been successfully treated (defined as a sustained virologic response or undetectable hepatitis C viral RNA levels at 12 or more weeks after the end of treatment) may be enrolled after discussion with the medical monitor.
13.	Subjects with a history of malignancy other than: 
 Non-metastatic basal or squamous cell carcinoma of the skin or carcinoma in situ that was surgically removed in total >1 year before signing the ICF and had not recurred Another type of malignancy that had been in remission for ≥ 5 years before signing the ICF and had not recurred
14.	Subjects with a history of myocardial infarction with residual atrial, nodal, or ventricular arrhythmias that are not controlled with medical and/or surgical intervention; second- or third-degree atrioventricular block; sick sinus syndrome; severe or unstable angina; or congestive heart failure within the last 12 months. A recent (≤ 12 months) history of myocardial infarction with secondary arrhythmias is exclusionary regardless of the therapeutic control.

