3.2.5. Columbia-Suicide Severity Rating Scale (C-SSRS)

Suicidality will be monitored during the trial using the C-SSRS. It was designed to quantify the severity of suicidal ideation and behavior.

This trial will use the “Baseline/Screening” and “Since Last Visit” versions of the scale. The “Baseline/Screening” version, which assesses the lifetime experience of the subject with suicide events and suicidal ideation and the occurrence of suicide events or ideation within a specified time period prior to entry into the trial, will be completed for all subjects at screening to determine eligibility and confirmed at baseline. Any subject with active suicidal ideation or suicidal behaviors within the last 6 months, suicidal behaviors within the last 2 years, or who in the clinical judgment of the investigator presents a serious risk of suicide should be excluded from the trial.

The “Since Last Visit” C-SSRS form will be completed at all visits after screening and baseline. The investigator will review the results of the “Since Last Visit” C-SSRS during the trial to determine whether it is safe for the subject to continue in the trial. If a subject demonstrates potential suicidal ideation associated with actual intent or method or plan as indicated by “YES” answers on item 4 or 5 of the C-SSRS, the investigator will evaluate whether a risk assessment by a qualified mental health professional (or the investigator alone if the investigator is a qualified mental health professional) is needed and whether the subject should continue in or be discontinued from the trial.

Details of C-SSR categories as well as definition of treatment emerging events are provided in [Section 9.3](#).

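### SAP 9.3 counts any post-baseline C-SSRS score above 0 as a treatment-emergent suicide-related event, while SAP 5.14.9 says that count rests on a comparison with baseline or lifetime history

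*SAP*

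**What the plan says.** SAP 5.14.9 plans three counts: suicide-related treatment-emergent events, treatment-emergent ideation, and suicidal behavior. It describes them as "based on a comparison of the C-SSRS at baseline and/or previous lifetime experience to maximum C-SSRS scores across all post-baseline assessments". SAP 3.2.5 sends the reader to Section 9.3 for how these are defined: C-SSRS categories "as well as definition of treatment emerging events are provided in" that section.

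Section 9.3 then defines the composite event. A subject qualifies "if at least one post-baseline suicidal ideation or suicidal behavior score is greater than 0". Neither baseline nor lifetime history enters.

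The other emergence definitions in 9.3 do look back:
- Treatment-emergent ideation applies "when there is at least one post-baseline suicidal ideation score > 0 and is an increase from baseline".
- The two serious-ideation categories require a baseline score below 4, or of 0, before a post-baseline score of 4 or 5.
- Emergence of behavior applies only "if there had been no suicidal behavior in Categories 6-10 reported at any pre-treatment assessment", lifetime history included.

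On eligibility, Protocol 5.2, exclusion 8, names subjects with Item 4 or 5 ideation "whose most recent episode meeting the criteria for C-SSRS Item 4 or Item 5 occurred within the last 6 months", any suicidal behavior in the last 2 years, and anyone the investigator considers a serious suicide risk. Protocol 8.3.3 and SAP 3.2.5 use a broader phrase that takes in active suicidal ideation generally within 6 months.

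**The concern.** A programmer working from 5.14.9 and one working from 9.3 would build different flags for the same table row. SAP 9.4 requires results to be verified by independent programming, so the ambiguity is a practical one.

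The definition in 9.3 also makes the row's label inaccurate. A subject with the same ideation score before and during treatment is reported as having a treatment-emergent suicide-related event, yet is not counted in the treatment-emergent ideation row of the same output. A reader of the study report could take the composite row as a count of new or worsened suicidality, when it also includes pre-existing ideation that did not worsen.

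**Working it through.** No sample size, power or error rate is involved, and the plan states no figure to reproduce. The check compares the two rules and lists the cases where they part.

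**Rules for ideation.** Let b be the baseline ideation score (recent history, prior 6 months) and m the maximum post-baseline ideation score, from 0 to 5.
- Section 9.3 composite rule: flag if m > 0.
- Baseline-compared rule, as in the 9.3 ideation definition and as 5.14.9 describes: flag if m > 0 and m > b.

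The rules differ exactly when 0 < m ≤ b, that is, when ideation was present before treatment and did not worsen.

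**Which baseline scores can be enrolled.**
- Exclusion 8 names only Items 4 and 5, so b can be 0, 1, 2 or 3, subject to the investigator's view of serious risk.
- Protocol 8.3.3, read literally, excludes all active ideation within 6 months. Category 1 is a wish to be dead and Category 2 is already active thoughts, so b can be 0 or 1.

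**Enumeration of (b, m) pairs.**

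| Baseline range | All pairs | Flagged by 9.3 | Flagged with comparison | Difference |
|---|---|---|---|---|
| b = 0 to 3 | 4 × 6 = 24 | 4 × 5 = 20 | 5 + 4 + 3 + 2 = 14 | 6 |
| b = 0 to 1 | 2 × 6 = 12 | 2 × 5 = 10 | 5 + 4 = 9 | 1 |

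In the first row the six pairs are three unchanged, (1,1), (2,2), (3,3), and three improved, (2,1), (3,1), (3,2). In the second row only (1,1) remains. So unchanged ideation can be counted under either eligibility text, while improved ideation can be counted only if exclusion 8 was the text applied.

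These are numbers of score patterns and say nothing about how often each occurs.

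**Behavior.** Exclusion 8 bars behavior in the last 2 years, and 9.3 takes the same 2 years as the behavior baseline. For an eligible subject, any post-baseline behavior is therefore an increase from recent history. Against lifetime history it need not be: a subject with behavior more than 2 years ago and again on treatment meets the composite rule but not the 9.3 behavior definition.

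**Overlap with another summary.** 5.14.9 already plans the post-baseline maximum over Categories 1-10. A maximum above 0 there identifies the same subjects as the composite rule in 9.3. As defined, the row repeats a planned summary, and 9.3 defines no baseline-compared composite of the kind 5.14.9 describes.

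**The case against.** The best defence is that the broad rule is deliberate. SAP 3.2.3.2 defines a treatment-emergent adverse event by timing alone. SAP 3.2.4.1 has two tiers for laboratory data: an abnormality is any out-of-range value after dosing starts, while a toxicity needs a rise in grade. Section 9.3 could follow that pattern, since its comparative categories say in their titles that they compare with recent or all prior history, and the composite does not. Post-baseline scores come from the form covering the interval since the last visit, so a positive score is not carried-over lifetime history. The sentence in 5.14.9 might also be parsed so that the comparison governs only the last item in its list.

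Part of this stands. A broad count is a legitimate summary and worth keeping under an accurate name. But the analogy does not remove the explicit sentence in 5.14.9, whose natural reading covers all three counts. The adverse-event parallel is also loose, because Protocol 8.4.1 sends occurrences that began before dosing to medical history.

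A reader might go further and infer that persisting cases mask a real suicidality signal by pulling the active-to-placebo ratio toward 1. The documents do not support that. C-SSRS results are summarized descriptively, with no ratio or test planned. If persistence adds the same rate p to arms with new-event rates a and c, the difference is (p + c) − (p + a) = c − a, which is unchanged. The baseline-compared ideation, serious-ideation and behavior counts remain, as does a full listing. Nor does the plan call the row drug-emergent or give it special prominence, and the rule applies to placebo as well.

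**Conclusion.** The inconsistency is real: the definition in 9.3 does not carry out the comparison that 5.14.9 says underlies this count. The effect is confined to one composite row. In all three arms that row can include subjects with unchanged pre-treatment ideation and, if Items 2-3 were enrolled under exclusion 8, subjects whose ideation improved.

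The size in subjects cannot be computed, because the documents give no rate of baseline or new-onset ideation. Any figure would rest on assumed rates. The direction is clear: the row can only be equal to or larger than the baseline-compared count. That persistence is equal across arms is an expectation from randomization, not something the documents show.

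Efficacy inference and the other C-SSRS emergence counts are untouched. This is a minor correction to a descriptive safety table.

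**What to change.** In SAP 9.3, define a treatment-emergent suicide-related event as either:
- (a) a post-baseline ideation score above 0 that is an increase from the recent-history baseline; or
- (b) post-baseline suicidal behavior (Categories 6-10), with its comparator stated as the prior 2 years or lifetime.

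The comparator in (b) must agree with 5.14.9 and be reconciled with the 9.3 behavior definition, which uses lifetime history. If 2 years is chosen, the SAP should say that the composite can include a recurrence of older behavior that the behavior row omits.

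Keep the present count, relabelled as any post-baseline suicidal ideation or behavior.

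The cost is one definition and one relabelled row, using C-SSRS data already collected. If the SAP is already final, its Section 6 provides for recording the change in the clinical study report.
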